6.1 Evaluation of efficacy (or Activity)

6.1.1 Definitions

Evaluable for toxicity

All patients will be evaluable for toxicity from the time of the first study drug administration.

6.2 Evaluation of Safety

Analyses will be performed for all patients receiving the radiotracer. The study will use the [CTCAE v4.0](#) for reporting of adverse events.

Any patient with Grade ≥ 3 hematologic toxicity will be followed with weekly CBC with differential until resolved to Grade 2 or lower.

6.3 Definition of Adverse Events

6.3.1 Adverse Event

An adverse event (also known as an adverse experience) is defined as any untoward medical occurrence associated with the use of a drug in humans, whether or not considered drug related. More specifically, an adverse event (can be any unfavorable and unintended sign (e.g., an abnormal laboratory finding), symptom, or disease temporally associated with the use of a drug, without any judgment about causality. An adverse event can arise from any use of the drug (e.g., off-label use, use in combination with another drug) and from any route of administration, formulation, or dose, including an overdose.

6.3.2 Adverse Reaction

An adverse reaction is defined as any adverse event caused by the use of a drug. Adverse reactions are a subset of all suspected adverse reactions for which there is reason to conclude that the drug caused the event.

6.3.2.1 Suspected

A suspected adverse reaction is defined as any adverse event for which there is a reasonable possibility that the drug caused the adverse event. For the purposes of IND safety reporting, “reasonable possibility” indicates that there is evidence to suggest a causal relationship between the drug and the adverse event. A suspected adverse reaction implies a lesser degree of certainty about causality than an adverse reaction.

6.3.2.2 Unexpected

An adverse event or suspected adverse reaction is considered *unexpected* if it is not listed in the investigator brochure or package insert(s), or is not listed at the specificity or severity that has been observed, or, if an investigator brochure is not required or available, is not consistent with the risk information described in the general investigational plan or elsewhere in the current application.

“Unexpected,” as used in this definition, also refers to adverse events or suspected adverse reactions that are mentioned in the investigator brochure as occurring with a class of drugs or as anticipated from the pharmacological properties of the drug, but are not specifically mentioned as occurring with the particular drug under investigation.

Adverse events that would be anticipated to occur as part of the disease process are considered *unexpected* for the purposes of reporting because they would not be listed in the investigator brochure. For example, a certain number of non-acute deaths in a cancer trial would be anticipated as an outcome of the underlying disease, but such deaths would generally not be listed as a suspected adverse reaction in the investigator brochure.

6.3.2.3 Serious

An adverse event or suspected adverse reaction is considered *serious* if, in the view of either the investigator or sponsor, it results in any of the following outcomes:

- Death
- Life-threatening adverse event
- Inpatient hospitalization or prolongation of existing hospitalization
- A persistent or significant incapacity or substantial disruption of the ability to conduct normal life function
- Congenital anomaly/birth defect
- Is a new cancer
- Is associated with an overdose

Important medical events that may not result in death, are life-threatening, or require hospitalization may be considered serious when, based upon appropriate medical judgment, they may jeopardize the patient or subject and may require medical or surgical intervention to prevent one of the outcomes listed in this definition. Examples of such medical events include allergic bronchospasm requiring intensive treatment in an emergency room or at home, blood dyscrasias or convulsions that do not result in inpatient hospitalization, or the development of drug dependency or drug abuse.

6.3.2.4 Life-threatening

An adverse event or suspected adverse reaction is considered life-threatening if, in the view of either the investigator or sponsor, its occurrence places the patient or subject at immediate risk of death. It does not include an adverse event or suspected adverse reaction that, had it occurred in a more severe form, might have caused death.

6.3.2.5 Attribution of Adverse Events

The toxicity profiles of the two investigational agents are largely non-overlapping, which should facilitate adverse event attribution to the specific agent. Hematologic toxicity will be attributed to Lu-PSMA-617 unless there is clear evidence of autoimmune cytopenia. Xerostomia will be attributed to Lu-PSMA-617 unless clear evidence of other autoimmune sequelae. Conversely, immune-related AEs such as colitis, pneumonitis, transaminitis will be attributed to pembrolizumab. In cases where attribution to a specific agent is not possible, the timing of onset in relation to timing of initiation of Lu-PSMA and pembrolizumab will be utilized. In cases where adverse event attribution to a single agent is not possible, attribution will be to study regimen

and dose modification criteria for both agents will be utilized. The PI will have the final determination of adverse event attribution that is reported.

AEs associated with pembrolizumab exposure, including coadministration with additional compounds, may represent an immunologic aetiology. These immune-related AEs (irAEs) may occur shortly after the first dose or several months after the last dose of pembrolizumab/combination treatment and may affect more than one body system simultaneously. Therefore, early recognition and initiation of treatment is critical to reduce complications. Based on existing clinical study data, most irAEs were reversible and could be managed with interruptions of pembrolizumab/combination treatment, administration of corticosteroids and/or other supportive care. For suspected irAEs, ensure adequate evaluation to confirm etiology or exclude other causes. Additional procedures or tests such as bronchoscopy, endoscopy, skin biopsy may be included as part of the evaluation. Dose modification and toxicity management guidelines for irAEs associated with pembrolizumab/combination treatment are provided in AE Table.

Attribution of Toxicity:

When study interventions are administered in combination, attribution of an adverse event to a single component is likely to be difficult. Therefore, while the investigator may attribute a toxicity event [to the combination, to ¹⁷⁷Lu-PSMA-617 alone or to pembrolizumab alone, for adverse events listed in AE Table 6, both interventions must be held according to the criteria in AE Table Dose Modification and Toxicity Management Guidelines for Immune-Related Adverse Events Associated with Pembrolizumab.

Holding Study Interventions:

When study interventions are administered in combination, if the AE is considered immune-related, both interventions should be held according to recommended dose modifications.

Restarting Study Interventions:

Participants may not have any dose modifications (no change in dose or schedule) of pembrolizumab in this study, as described in AE Table.

- If the toxicity does not resolve or the criteria for resuming treatment are not met, the participant must be discontinued from all study interventions.
- If the toxicities do resolve and conditions are aligned with what is defined in AE Table, the combination of ¹⁷⁷Lu-PSMA-617 and pembrolizumab may be restarted at the discretion of the investigator. In these cases where the toxicity is attributed to the combination or to ¹⁷⁷Lu-PSMA-617 alone, re-initiation of pembrolizumab as a monotherapy may be considered at the principal investigator's discretion .

6.4 Recording of an Adverse Event

All grade 3 and above adverse events will be recorded using the NCI CTCAE v4.0. The Investigator will assign attribution of the possible association of the event with use of the investigational drug.

Relationship	Attribution	Description
Unrelated to investigational drug/intervention	Unrelated	The AE is clearly NOT related to the intervention
	Unlikely	The AE is doubtfully related to the intervention
Related to investigational drug/intervention	Possible	The AE may be related to the intervention
	Probable	The AE is likely related to the intervention
	Definite	The AE is clearly related to the intervention

Signs or symptoms reported as adverse events will be graded and recorded by the Investigator according to the CTCAE. When specific adverse events are not listed in the CTCAE they will be graded by the Investigator as *none*, *mild*, *moderate* or *severe* according to the following grades and definitions:

- Grade 0 No AE (or within normal limits)
- Grade 1 Mild; asymptomatic or mild symptoms; clinical or diagnostic observations only; intervention not indicated
- Grade 2 Moderate; minimal, local, or noninvasive intervention (e.g., packing, cauter) indicated; limiting age-appropriate instrumental activities of daily living (ADL)
- Grade 3: Severe or medically significant but not immediately life-threatening; hospitalization or prolongation of hospitalization indicated; disabling; limiting self-care ADL
- Grade 4: Life-threatening consequences; urgent intervention indicated
- Grade 5: Death related to AE

6.5 Follow-up of Adverse Events

All adverse events will be followed with appropriate medical management until resolved. Patients removed from study for unacceptable adverse events will be followed until resolution or stabilization of the adverse event. For selected adverse events for which administration of the investigational drug was stopped, a re-challenge of the subject with the investigational drug may be conducted if considered both safe and ethical by the Investigator.

6.6 Expedited Reporting

Reporting to the Data and Safety Monitoring Committee

If a death occurs during the treatment phase of the study or within 30 days after the last administration of the study drug(s) and it is determined to be related either to the study drug(s) or to a study procedure, the Investigator or his/her designee must notify the DSMC Chair (or qualified alternate) within 1 business day of knowledge of the event. The contact may be by phone or e-mail.

Reporting to UCSF Institutional Review Board

The Principal Investigator must report events meeting the UCSF IRB definition of “Unanticipated Problem” (UP) within 10 business days of his/her awareness of the event.

Expedited Reporting to the Food and Drug Administration

If the study is being conducted under an IND, the Sponsor-Investigator is responsible for determining whether or not the suspected adverse reaction meets the criteria for expedited reporting in accordance with Federal Regulations (21 CFR §312.32).

The Investigator must report in an IND safety report any suspected adverse reaction that is both serious and unexpected. The Sponsor-Investigator needs to ensure that the event meets all three definitions (Section 7.3):

- Suspected adverse reaction
- Unexpected
- Serious

If the adverse event does not meet all three of the definitions, it should not be submitted as an expedited IND safety report.

The timeline for submitting an IND safety report to FDA is no later than **15 calendar days** after the Investigator determines that the suspected adverse reaction qualifies for reporting (21 CFR 312.32(c)(1)).

Any unexpected fatal or life-threatening suspected adverse reaction will be reported to FDA no later than **7 calendar days** after the Investigator's initial receipt of the information (21 CFR 312.32(c)(2)).

Any relevant additional information that pertains to a previously submitted IND safety report will be submitted to FDA as a Follow-up IND Safety Report without delay, as soon as the information is available (21 CFR 312.32(d)(2)).

Expedited Reporting to Merck

For the time period beginning at treatment allocation/randomization through 90 days following cessation of treatment, or 30 days following cessation of treatment if the participant initiates new anticancer therapy, whichever is earlier, any serious adverse event, or follow up to a serious adverse event, including death due to any cause whether or not related to the Merck product, must be reported within 2 working days to Merck [REDACTED].

Additionally, any serious adverse event, considered by an investigator who is a qualified physician to be related to Merck product that is brought to the attention of the investigator at any time following consent through the end of the specified safety follow-up period specified in the paragraph above, or at any time outside of the time period specified in the previous paragraph also must be reported immediately to Merck [REDACTED].

All participants with serious adverse events must be followed up for outcome.

SAE reports and any other relevant safety information are to be forwarded to the Merck Global Safety facsimile [REDACTED]

A copy of all 15 Day Reports and Annual Progress Reports is submitted as required by FDA. Investigators will cross reference this submission according to local regulations to the Merck

Investigational Compound Number (IND, CSA, etc.) at the time of submission. Additionally investigators will submit a copy of these reports to Merck & Co., Inc. [REDACTED] [REDACTED] the time of submission to FDA.

Expedited Reporting to PrimeVigilance

All AEs, SAEs, and SUSARs, related to ¹⁷⁷Lu-PSMA-617 will be reported to:

PrimeVigilance
[REDACTED]
[REDACTED]
[REDACTED]
[REDACTED]

SAEs and SUSARs must be reported to PrimeVigilance within 2 working days.

Definition of an Overdose for This Protocol and Reporting of Overdose to the Sponsor and to Merck

For purposes of this study, an overdose of pembrolizumab will be defined as any dose of 1,000 mg or greater (≥ 5 times the indicated dose). No specific information is available on the treatment of overdose of pembrolizumab. In the event of overdose, the participant should be observed closely for signs of toxicity. Appropriate supportive treatment should be provided if clinically indicated.

If an adverse event(s) is associated with ("results from") the overdose of a Merck product, the adverse event(s) is reported as a serious adverse event, even if no other seriousness criteria are met.

If a dose of Merck's product meeting the protocol definition of overdose is taken without any associated clinical symptoms or abnormal laboratory results, the overdose is reported as a non-serious Event of Clinical Interest (ECI), using the terminology "accidental or intentional overdose without adverse effect."

All reports of overdose with and without an adverse event must be reported within 24 hours to the Sponsor and within 2 working days hours to Merck [REDACTED]
[REDACTED]

Events of Clinical Interest

Selected non-serious and serious adverse events are also known as Events of Clinical Interest (ECI) and must be reported within 2 working days to Merck [REDACTED]
[REDACTED].

For the time period beginning when the consent form is signed until treatment allocation/randomization, any ECI, or follow up to an ECI, that occurs to any participant must be reported within 2 working days to Merck [REDACTED] if it causes the participant to be excluded from the trial, or is the result of a protocol-specified intervention, including but not limited to washout or discontinuation of usual therapy, diet, placebo treatment or a procedure.

For the time period beginning at treatment allocation/randomization through 90 days following cessation of treatment, or 30 days following cessation of treatment if the participant initiates new anticancer therapy, whichever is earlier, any ECI, or follow up to an ECI, whether or not related to Merck product, must be reported within 2 working days to Merck [REDACTED].

Events of clinical interest for this trial include:

1. an overdose of Merck product, as defined above, that is not associated with clinical symptoms or abnormal laboratory results.
2. an elevated AST or ALT lab value that is greater than or equal to 3X the upper limit of normal and an elevated total bilirubin lab value that is greater than or equal to 2X the upper limit of normal and, at the same time, an alkaline phosphatase lab value that is less than 2X the upper limit of normal, as determined by way of protocol-specified laboratory testing or unscheduled laboratory testing.*

***Note:** These criteria are based upon available regulatory guidance documents. The purpose of the criteria is to specify a threshold of abnormal hepatic tests that may require an additional evaluation for an underlying etiology.

7 Measurement of Response

Response and progression will be evaluated in this study using the international criteria proposed by the Response Evaluation Criteria in Solid Tumors (RECIST) 1.1 criteria, with use of PCWG criteria for assessment of new/pre-existing bone lesions. Changes in only the longest diameter (unidimensional measurement- LD) of the tumor lesions are used in the RECIST criteria.

Note: lesions are either measurable or non-measurable using the criteria provided below. The term “evaluable” in reference to measurability will not be used because it does not provide additional meaning or accuracy. All measurements should be taken and recorded in metric notation using a ruler or calipers. All baseline evaluations should be performed as closely as possible to the beginning of treatment and never more than 30 days before the beginning of the treatment. The same method of assessment and the same technique should be used to characterize each identified and reported lesion at baseline and during follow-up. Imaging-based evaluation is preferred to evaluation by clinical examination when both methods have been used to assess the antitumor effect of a treatment.

Clinical lesions. Clinical lesions will only be considered measurable when they are superficial (e.g., skin nodules and palpable lymph nodes). In the case of skin lesions, documentation by color photography, including a ruler to estimate the size of the lesion, is recommended.

Chest x-ray. Lesions on chest x-ray are acceptable as measurable lesions when they are clearly defined and surrounded by aerated lung. However, CT is preferable.

Conventional CT and MRI. These techniques should be performed with cuts of 10 mm or less in slice thickness contiguously. Spiral CT should be performed using a 5 mm contiguous reconstruction algorithm. This applies to tumors of the chest, abdomen, and pelvis. Head and neck tumors and those of extremities usually require specific protocols.

7.1 Measurable disease/ Target lesions

All measurable lesions (lesions that can be accurately measured in at least one dimension [longest diameter to be recorded] as ≥ 10 mm with spiral CT) up to a maximum of 2 lesions per organ and 5 lesions total, representative of all involved organs, should be identified as target lesions and recorded and measured at baseline. Target lesions should be selected on the basis of their size (lesions with the longest diameter) and the suitability for accurate repeated measurements (either by imaging techniques or clinically). A sum of the longest diameter (LD) for all target lesions will be calculated and reported as the baseline sum LD. The baseline sum LD will be used as a reference by which to characterize the objective tumor response.

Lymph node metastases must measure 1.5 cm or greater in short axis diameter to be considered target lesions, while other target lesions must measure 1 cm or greater (with spiral CT scans).¹⁷

Complete Response (CR):	Disappearance of all target lesions
Partial Response (PR):	At least a 30% decrease in the sum of the longest diameter (LD) of target lesions, taking as reference the baseline sum LD
Progressive Disease (PD):	At least a 20% increase in the sum of the LD of target lesions, taking as reference the smallest sum LD recorded since the treatment started (including baseline LD), or the appearance of one or more new lesions
Stable Disease (SD):	Neither sufficient shrinkage to qualify for PR nor sufficient increase to qualify for PD, taking as reference the smallest sum LD since the treatment started (including

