2.2 Endpoints

2.2.1 Primary Endpoint

Part A: Safety profile of ¹⁷⁷Lu-PSMA-617 in combination with pembrolizumab as graded by CTCAE criteria.

Part B: Objective response rate by RECIST 1.1 criteria

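### Nodal targets are selected by short axis but scored by longest diameter, so the Part B response rate may not be the RECIST 1.1 rate that the plan names

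*Combined protocol and SAP*

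**What the plan says.** Section 2.2.1 gives the primary endpoint as "Part B: Objective response rate by RECIST 1.1 criteria". Section 8.4.1 likewise defines response as a confirmed CR or PR under RECIST v1.1, and inclusion criterion 14 requires measurable disease by the same standard.

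Section 7 opens by adopting that standard: "Response and progression will be evaluated in this study using the international criteria proposed by the Response Evaluation Criteria in Solid Tumors (RECIST) 1.1 criteria". The same paragraph then says: "Changes in only the longest diameter (unidimensional measurement- LD) of the tumor lesions are used in the RECIST criteria".

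Section 7.1 holds the working rules:

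- Nodal selection: "Lymph node metastases must measure 1.5 cm or greater in short axis diameter to be considered target lesions".
- Baseline: "A sum of the longest diameter (LD) for all target lesions will be calculated and reported as the baseline sum LD".
- CR: "Disappearance of all target lesions".
- PR: "At least a 30% decrease in the sum of the longest diameter (LD) of target lesions, taking as reference the baseline sum LD".
- PD: "At least a 20% increase in the sum of the LD of target lesions, taking as reference the smallest sum LD recorded" since treatment started, or new lesions.

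No section gives a separate scoring rule for nodes, a nodal size threshold for CR, or a minimum in millimetres for PD. No section says whether Section 7.1 or the published criteria prevail if they differ.

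**The concern.** A node qualifies as a target on one dimension, and its response is judged on another. A node need not shrink in proportion on both axes, so the choice of axis can decide whether the 30% threshold for PR is met.

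A reader who follows Section 7.1 sums longest diameters. A reader who takes RECIST 1.1 as governing would go to the published criteria, and the protocol does not help there. Its reference list has no RECIST publication, and the superscript 17 beside the nodal rule leads to a PSMA PET imaging study. In an open-label, single-centre study, leaving the rule unsettled also leaves room to choose it after the scans have been seen.

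Part A is affected as well. Section 1.7.1 cites 3 responses in 6 patients among its reasons for raising the expansion from 12 to 25, and Section 8.4.1 selects dose and schedule from aggregate safety and efficacy.

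**Working it through.** **1. The plan's own figure.** Section 8.1 gives N = 25, 10% against 40%, two-sided 0.05 and 93% power. Taking an exact binomial test with the upper tail limited to 0.025:

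- P(X ≥ 6 | 0.10) = 0.0334, which is too large.
- P(X ≥ 7 | 0.10) = 0.0095, so the cut-off is 7 of 25.
- Power = P(X ≥ 7 | 0.40) = 0.926.

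The stated 93% reproduces. It does not depend on the nodal rule, but it shows where a single patient matters.

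**2. Effect of the axis.** Percentage change = (follow-up - baseline) / baseline. Node sizes are assumed (short axis x longest diameter), with the node as the only target.

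| Node | Short axis | Longest diameter |
|---|---|---|
| 16 x 24 to 9 x 18 mm | (9 - 16)/16 = -44%: meets the PR threshold | (18 - 24)/24 = -25%: SD |
| 15 x 20 to 11 x 14 mm | (11 - 15)/15 = -27%: SD | (14 - 20)/20 = -30%: PR |

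Both nodes satisfy the 1.5 cm entry rule. The axis moves the first patient out of response and the second into it.

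**3. Effect on the primary endpoint.** One patient is 1/25 = 4 points in Part B. Exact (Clopper-Pearson) 95% intervals:

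- 7/25 = 28%: 12.1% to 49.4%, which excludes the 10% control.
- 6/25 = 24%: 9.4% to 45.1%, which does not.

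If the scoring rule shifted the true ORR, power at the 7-of-25 cut-off would be 97.4% at 45%, 92.6% at 40%, 82.7% at 35% and 65.9% at 30%. These values illustrate sensitivity; the documents give no basis for choosing among them. In the Part A figure of 3/6, one patient is 1/6 = 17 points.

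**4. CR wording.** Section 8.4.1 counts CR and PR alike. A patient whose node stays visible while the sum falls by 30% or more is a PR under Section 7.1, and so still a responder. The wording by itself moves patients between CR and PR and leaves ORR unchanged.

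**5. PD minimum.** The PD threshold is 0.20 x nadir sum: 2 mm at 10 mm, 3 mm at 15 mm, 4 mm at 20 mm. If a floor of 5 mm is assumed (none is given), it would matter only below 5/0.20 = 25 mm. It could change ORR only where a small rise is called PD before a later confirmed response. Its main effect is on duration of response (Section 7.5) and radiographic progression-free survival (Section 8.4.2).

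**The case against.** The strongest defence is that RECIST 1.1 is named in Sections 2.2.1, 7 and 8.4.1 and in the eligibility criteria, so it may govern in practice whatever Section 7.1 says. The documents do not show how scans are read. This stands against any statement that the reported ORR *is not* the RECIST 1.1 ORR. It does not remove the conflict, because no precedence is stated.

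Second, Section 7.1 is workable as written. Short axis serves only as an entry threshold, and all change is then measured on longest diameter. That is fair, but a workable rule is not necessarily the named one.

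Third, the examples are hypothetical single-node cases. Section 7.1 sums up to five targets, which can dilute one node's effect, and the documents do not say how many patients have nodal targets. This stands, and it is why no net bias is claimed.

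Fourth, Part B seeks a preliminary estimate in a phase 1b study, reported descriptively with a confidence interval. That limits the consequences, but an estimate still needs one definition.

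A reader might also infer that the CR wording lowers ORR, or that the missing PD minimum produces false progression in the best responders. Steps 4 and 5 do not support the first. For the second, the documents give no measurement error for diameters, so the frequency of spurious 2-3 mm rises is unknown, and the confirmatory scans in Sections 3.4 and 5.1 offer some protection. Nor does CR alone decide access to second-course treatment: Section 5.1 also has a route for SD, PR or CR after 35 administrations.

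**Conclusion.** The point holds for the measurement axis. The primary endpoint names one standard, while the working rules select nodes by short axis and score them by longest diameter, with no order of precedence. The reported ORR may therefore differ from the RECIST 1.1 ORR, by 4 points for each reclassified Part B patient and in either direction. Near the cut-off, one patient settles whether the interval excludes 10%.

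The axis mismatch within Section 7.1 is visible in the documents alone. The illustrations rest on assumed node sizes. The text of RECIST 1.1 is not in the documents, so how far Section 7.1 departs from it has to be checked against the published criteria. The missing nodal CR rule and PD minimum are real gaps but secondary: the first bears on CR against PR, the second mainly on duration of response and radiographic progression-free survival at small nadir sums.

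**What to change.** - Rewrite Section 7.1 so that nodal targets are both selected and summed by short axis, and non-nodal targets are summed by longest diameter. Word the baseline, PR and PD rules as a sum of diameters on that basis.
- Remove the sentence at the start of Section 7 that limits measurement to the longest diameter.
- Bring the nodal rule for CR and the absolute minimum for PD into line with RECIST 1.1, taking the thresholds from the published criteria, and cite that publication.
- State that RECIST 1.1 governs if the texts differ.
- Apply the same rule to all Part A and Part B scans, including those behind the 3/6 figure in Section 1.7.1.
- Section 8.4.3 also scores lesion response by longest diameter. Conform it, or say that the difference is intended.

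The cost is protocol wording and re-measurement of nodal targets on existing scans. No new imaging or patients are needed, and the sample size does not change.
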